 - c. Real-world time to treatment discontinuation (rwTTD) from the start of the first-line therapy at time points 3, 6, 12, 18, 24, 30, and 36 months.
 - d. Real-world time to next treatment (rwTTNT) from the start of the first-line therapy at time points 3, 6, 12, 18, 24, 30, and 36 months.
 - e. Real-world time to chemotherapy (rwTTC) from the start of the first-line therapy at time points 3, 6, 12, 18, 24, 30, and 36 months.
 - f. Real-world time to dose adjustment (rwTTDA) from the start of the first-line therapy at time points 3, 6, 12, 18, 24, 30, and 36 months.

5.1 Definitions/Derivations for Demographic, Clinical characteristics, treatment pattern and Efficacy/Effectiveness Endpoint(s)

- Age at initial diagnosis, A/MBC diagnosis, at start of palbociclib treatment and death. - They will be categorized into age categories: <50, 50-64, 65 –74, ≥75 years.
- Time to metastasis- It is defined as months between initial and metastasis diagnoses. It will be categorized into ≤12 months, 13-24 months, 25-36 months,>36 months and de novo metastatic.
- Disease Free Interval (DFI)- It is defined as months from the end of adjuvant therapy to the date of disease recurrence. It will be categorized into ≤12 months, 13-24 months, 25-36 months,>36 months and Unknown.
- Line of therapy- The line number (1; 2; 3; etc.) in the A/MBC setting will be assigned based on Syapse line of therapy algorithm.
- Regimen medication(s)- Systemic therapies included in line regimen defined by Syapse line of therapy algorithm.
- Time to first dose change- It is defined as days from palbo dose 1 start date to palbo dose 2 start date, if applicable.
- Number of dose changes- Number of dose reduction(s) and number of dose increases over the calendar time (quarter since February 2015) and over treatment cycle since palbo dose 1 start date.
- Real-world Overall Survival (rwOS)- It is defined as length of time from the start of palbociclib + AI treatment to the earliest of the following: date of death, date of last contact, or the end of study period
- Real-world progression free survival (rwPFS)- It is defined as length of time from the start of palbociclib + AI treatment to the earliest of the following: clinician-assessed progression event (sources include medical oncology consult/note, radiation oncology note and discharge summary), date of death, date of initiation

PFIZER CONFIDENTIAL

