of the 2nd line for patients with >1 line of therapy, date of last contact, or end of study period.

- Real world time to treatment discontinuation (rwTTD)- It is defined as length of time from the start of palbociclib + AI treatment to the earliest of the following: date the patient discontinues first-line treatment, date of death, last known usage of first-line treatment, or end of study period.
- Real world time to next treatment (rwTTNT)- It is defined as length of time from the start of palbociclib + AI treatment to the earliest of the following: subsequent line of therapy initiation, date of death, date of last contact, or end of the study period.
- Real world time to chemotherapy (rwTTC)- It is defined as length of time from the start of palbociclib + AI treatment to the earliest of the following: the day before the start of subsequent chemotherapy for patients with evidence of chemotherapy, or date of death for any reason. Or, where censored, the latest of date of last contact, or end of the study period.
- Real world time to dose adjustment (rwTTDA)- It is defined as length of time from the start of palbociclib + AI treatment to the earliest of the following: date of first-line treatment dose adjustment, date of death, date of first-line treatment discontinuation, date of last contact or end of study period.

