Kaplan-Meier survival analysis is used to descriptively characterize time to event outcomes. In this study, following time to event outcomes will be analyzed-

- Time to Real-world overall survival (rwOS)

[figure not shown]
The time origin for analysis of rwOS is start of the first-line therapy, and the terminal event is death. For patients not known to be deceased at the time of analysis, rwOS will be censored at the earliest of the last date of last contact or the end of the study period.

- Time to Real-world progression-free survival (rwPFS)

The time origin for analysis of rwPFS is start of the first-line therapy. Patients without a clinician-assessed progression event or death will be censored at the earliest of the following events: date of initiation of the 2nd line for patients with >1 line of therapy, date of last contact, or end of study period.

- Real world time to treatment discontinuation (rwTTD)

PFIZER CONFIDENTIAL

The time origin for analysis of rwTTD is start of the first-line therapy. Patients without first-line treatment discontinuation and who did not die will be censored at the earliest of the following events: last known usage of first-line treatment, or end of study period.

- Real world time to next treatment (rwTTNT)

The time origin for analysis of rwTTNT is start of the first-line therapy. Patients without a subsequent line of therapy initiation and who did not die will be censored at the earliest of the following events: date of last contact, or end of the study period.

- Real world time to chemotherapy (rwTTC)

The time origin for analysis of rwTTC is start of the first-line therapy. Patients who did not receive subsequent chemotherapy and who did not die will be censored at the latest of the following events: date of last contact, or end of the study period.

- Real world time to dose adjustment (rwTTDA)

The time origin for analysis of rwTTDA is start of the first-line therapy. Patients without a first-line treatment dose adjustment will be censored at the earliest of the following events: first-line treatment discontinuation, date of death, date of last contact, or end of the study period.

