Therapy start date	Year, month, day
Therapy end date	Year, month, day
Start reason	Recurrence; Progression; Other reason not related to worsening disease
Start reason source date	Year, month, day (can be linked to clinician confirmation date of recurrence/progression if start reason is recurrence/progression)
Stop reason	Categories including: Progression; Toxicity; End of planned therapy; Insurance changes; Treatment ongoing; Other
Stop reason source date	Year, month, day (can be linked to clinician confirmation date of recurrence/progression if stop reason is recurrence/progression)
Treatment part of clinical trial	Yes; No
Palbociclib-specific variables (captured in addition to above variables)	
Combination AI partner	Letrozole, Anastrozole, Exemestane
Concomitant LHRH Agonists	Goserelin (Zoladex), Histrelin (Vantas), Leuprolide (Eligard, Lupron), Triptorelin (Trelstar)
Dose 1 (start dose)	125mg, 100mg, 75mg
Dose 1 start date	Year, month, day
Dose n (where n>=2)	125mg, 100mg, 75mg
Dose n start date	Year, month, day
Dose n adjustment type or reason	Categories include schedule change; dose delay; hold; cost; patient refusal; toxicity

Variables that will be derived from curated data will include the following:

Data Elements	Description
-----------------------------	---------------------------

PFIZER CONFIDENTIAL

Age at A/MBC diagnosis	Age in years; age categories: <50, 50-64, 65 –74, ≥75 years (Exact list will depend on the expert de-ID approach)
Age at start of palbociclib treatment	Age in years; age categories: <50, 50-64, 65 –74, ≥75 years
Date of death	If patient vital status = deceased, date of death from the medical record (capturing from EMR, registries, third party integrations) (Availability of the exact date will depend on the Expert de-ID approach)
Palbo dose change ever	Yes; No
Disease Free Interval (DFI)	Months from the end of adjuvant therapy to the date of disease recurrence ≤12 months, 13-24 months, 25-36 months >36 months Unknown
Endocrine sensitivity	≥12 months without recurrence/progression after completion of endocrine therapy in the adjuvant setting

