Real-world progression free survival (rwPFS)	Length of time from the start of palbociclib + AI treatment to the earliest of the following: clinician-assessed progression event, date of death, date of last contact, or end of study period. Progression identified from tissue/pathology or imaging/radiology and confirmed by clinician (in 2 separate data points), from MA guidance: 
1. Medical Oncology Consult/Note (can also include medical oncologist history and physical (H&P))2. Radiation Oncology note/consult/(can also include radiation oncology H&P)3. Progress Note (can also include /H&P/Consult - use this option for physician of other discipline in the absence of numbers 1 and 2)4. Discharge Summary5. Nursing Note6. Care Everywhere/Scanned Documents/External lab reports (for information diagnosed outside of facility for which patient is being abstracted)7. Other
Real world time to treatment discontinuation (rwTTD)	Length of time from the start of palbociclib + AI treatment to the earliest of the following: date the patient discontinues first-line treatment, date of death, last known usage of first-line treatment, or end of study period
Real world time to next treatment (rwTTNT)	Length of time from the start of palbociclib + AI treatment to the earliest of the following: subsequent line of therapy initiation, date of death, date of last contact, or end of the study period

Real world time to dose adjustment (rwTTDA)	Length of time from the start of palbociclib + AI treatment to the earliest of the following: date of first-line treatment dose adjustment, date of death, last known usage of first-line treatment, or end of study period.
Real world time to chemotherapy (rwTTC)	Length of time from the start of palbociclib + AI treatment to the earliest of the following: the day before the start of subsequent chemotherapy for patients with evidence of chemotherapy, or date of death for any reason. Or, where censored, the latest of date of last contact, or end of the study period.

PFIZER CONFIDENTIAL

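### rwTTDA can only record palbociclib dose changes, but its risk period ends with a two-drug first-line treatment whose discontinuation is not defined by drug

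*SAP*

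**What the plan says.** **Event.** Section 5.1 measures time to first dose change as "days from palbo dose 1 start date to palbo dose 2 start date, if applicable". In Appendix 2 (Section 9.2), dose levels, their start dates and the adjustment type or reason stand under "Palbociclib-specific variables (captured in addition to above variables"). The adjustment field reads: "Categories include schedule change; dose delay; hold; cost; patient refusal; toxicity". No such fields exist for the AI.

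**End of the risk period.** There are two wordings:

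- Section 5.1 runs rwTTDA to the earliest of "date of first-line treatment dose adjustment, date of death, date of first-line treatment discontinuation, date of last contact or end of study period". Section 7.2 makes all of these dates except the adjustment censoring dates: "Patients without a first-line treatment dose adjustment will be censored at the earliest of the following events: first-line treatment discontinuation", and so on.
- Appendix 2 runs it to the earliest of "date of first-line treatment dose adjustment, date of death, last known usage of first-line treatment, or end of study period". This drops the discontinuation date and last contact, and adds last known usage.

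**rwTTD.** Section 5.1 uses the same undivided term: time to the earliest of "date the patient discontinues first-line treatment, date of death, last known usage of first-line treatment, or end of study period".

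**The line.** First-line treatment is palbociclib + AI. Section 5.1 takes the line number and the drugs in the regimen from the Syapse line of therapy algorithm. The SAP does not give that algorithm's rule for a dropped component. The rwTTDA tables in Section 8.2.1 are labelled as using regimen-based lines.

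**The concern.** The event belongs to one drug and the risk period to a two-drug regimen. A patient who permanently stops palbociclib and stays on the AI can no longer have a palbociclib dose adjustment. If first-line treatment is taken to continue while the AI continues, that patient remains in the Kaplan-Meier denominator until the AI also stops, and can never contribute an event. The estimated hazard of adjustment falls and the adjustment-free curve rises. Under Appendix 2, the last known usage of first-line treatment could likewise be the last AI record.

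rwTTDA is listed among the primary objectives and endpoints, with a median and confidence interval, landmark estimates and a Cox model. The study is descriptive, so these estimates are its results. Two analysts working from this text could treat the same patient as censored at the palbociclib stop, as still at risk or, if the stop is coded as a hold, as having an event.

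**Working it through.** **1. Is there a planned figure to reproduce?** No. The SAP gives no expected median, event count or rate for rwTTDA or rwTTD, and Section 3 (hypotheses) is not applicable. Everything below is illustrative, and every rate is an assumption.

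**2. Model.** All times are exponential, in months. While on palbociclib, the hazards are λ for a dose adjustment, μ for stopping both drugs and δ for stopping palbociclib alone. After a palbociclib-only stop, the AI ends at hazard ν. Administrative censoring is independent (6 to 60 months, uniform), so it does not move the large-sample curve.

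Let κ = λ + μ + δ. Among patients without an adjustment, the AI-alone group relative to those on palbociclib at time t is

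R(t) = δ(e^((κ−ν)t) − 1)/(κ − ν).

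If risk lasts until both drugs stop, the Kaplan-Meier hazard is λ/(1 + R(t)). The median T solves ∫₀ᵀ λ/(1 + R(t)) dt = ln 2 = 0.693. If risk ends at the palbociclib stop, R = 0 and the median is 0.693/λ.

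**3. First set of assumptions:** λ = 0.03, μ = 0.04, ν = 1/12 = 0.0833.

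With risk ended at the palbociclib stop, the median is 0.693/0.03 = 23.1 months.

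For δ = 0.01, κ = 0.08 and κ − ν = −0.00333. Then R(24) = 0.01 × (0.9231 − 1)/(−0.00333) = 0.231, so 0.231/1.231 = 18.7% of the risk set at 24 months is on the AI alone. With R(t) ≈ 0.01t, the integral is 3 ln(1 + 0.01T). Setting it to 0.693 gives T = 100(e^0.231 − 1) = 26.0; the exact solution is 25.9.

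The share seen to stop palbociclib alone is (δ/s) × [1 − (e^(−6s) − e^(−60s))/(54s)] with s = μ + δ. For δ = 0.01 this is 0.2 × 0.744 = 14.9%.

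| δ per month | Seen to stop palbociclib alone | AI-alone share of risk set at 24 months | Median, risk until both drugs stop | Median, risk to palbociclib stop | Rise |
|---|---|---|---|---|---|
| 0.005 | 7.9% | 9.8% | 24.4 | 23.1 | 1.3 |
| 0.01 | 14.9% | 18.7% | 25.9 | 23.1 | 2.8 |
| 0.02 | 26.4% | 34.2% | 29.8 | 23.1 | 6.7 |

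Simulation with 400,000 patients per scenario agrees within about 0.2 month.

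**4. Second set of assumptions:** median time to adjustment 12 or 24 months, median palbociclib duration 15 or 20 months, 5% to 30% of palbociclib stoppers continuing the AI alone for a median of 12 months. Simulated medians under the both-drugs reading:

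- True median 12: from 12.1 (5% continuing) to 13.3 (30%).
- True median 24: from 24.4 (5%) to 29.4 (30%).
- With 0% continuing, the two rules agree.

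Across both sets, the rise runs from about 0.1 to 6.7 months.

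**5. rwTTD under the first set.** Median time to the palbociclib stop is 0.693/s: 15.4, 13.9 and 11.6 months for the three δ values. Median time until both drugs stop is 16.7, 16.2 and 15.4. These are two different quantities. The gap shows what the unstated definition decides; it is not an error in either.

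**The case against.** A reader might infer that the SAP keeps AI-alone patients at risk until the whole regimen ends, so that rwTTDA is biased upward as written. The document does not support this. It never says that both drugs must stop. A patient on the AI alone is no longer on palbociclib + AI, so dropping palbociclib can be read as discontinuing first-line treatment. Some passages lean that way: Table 15.4.5 sets discontinuation and its reasons beside palbociclib dose adjustment, and the treatment-pattern objective in Section 2.2 puts discontinuation in parentheses after time to dose adjustment. Regimen-based lines may also mean that a dropped component closes the line. Under any of these readings the effect is zero. This part of the objection stands, and it limits the point to an undefined term with a possible bias.

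A reader might also infer that rwTTD is wrongly lengthened by AI-only months. That would follow only if the target were palbociclib duration, or time with both drugs in use. The SAP states neither, and whole-regimen duration is a legitimate quantity.

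On size, in simulations of 350 patients (300 to 400 are expected), the 95% sampling range of the palbociclib-end median was about 19 to 30 months in the two lower scenarios of the first set. Shifts of 1.3 and 2.8 months lie well inside that range. Under the both-drugs reading, however, the shift is systematic and a larger sample would not remove it.

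The algorithm does not settle the matter from outside the SAP. If dropping palbociclib did open a new line, AI alone would count as a next treatment for rwTTNT and would trigger the second-line censoring of rwPFS. That consequence also deserves to be stated.

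**Conclusion.** The point holds as a definitional gap with a possible bias in one direction. The rwTTDA event is specific to palbociclib, and its risk period is tied to a regimen whose discontinuation is not defined by component. The two wordings of the end dates also differ.

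If AI-alone patients are kept at risk, the adjustment-free curve is too high, and the illustrative rise in the median is about 0.1 to 7 months. The largest figure needs about a quarter of patients to stop palbociclib alone. If the palbociclib stop already ends the risk period, the effect is nil. None of the rates behind these figures comes from the SAP.

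For rwTTD, the finding is only that the component is not stated. No hypothesis test or decision rule depends on either endpoint, so the consequence is confined to the reported estimates. The change is still worth making, because it aligns event and risk set whichever reading was intended.

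**What to change.** 1. In Sections 5.1 and 7.2 and in Appendix 2, end the rwTTDA risk period at the palbociclib therapy end date in place of first-line treatment discontinuation or last known usage. Appendix 2 already captures start and end dates for each therapy.
2. State whether a permanent palbociclib stop is an rwTTDA event, a competing event or a censoring date, and how it is told apart from a hold. Censoring assumes that stoppers would have had the same adjustment hazard as those who continued; a competing event calls for cumulative incidence.
3. Use one list of end dates in all three places, resolving the difference between Appendix 2 and Sections 5.1 and 7.2 over last contact and last known usage.
4. For rwTTD, state whether discontinuation means the first drug stopped or the whole regimen. Reporting palbociclib duration beside regimen duration is optional.
5. State the line algorithm's rule for a dropped component, since rwTTNT and rwPFS depend on it too.

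The cost is a few lines of wording and some programming, with no new data. The reported median rwTTDA may come out somewhat shorter than under a whole-regimen risk period.

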7.2.1 Safety Analyses

Not Applicable.

7.2.2 Summary of Analyses of the Study Outcomes

Outcome	Analysis Set	Supports Protocol Objective Number	Subgroup	Statistical Method	Factors/Covariates/Strata	Missing Data
Summary of Demographic Characteristics	All patients meeting inclusion and exclusion criteria	1a	None	Frequency and percentage of subjects	Not Applicable	Numbers reported
Summary of clinical characteristics and comorbidities	All patients meeting inclusion and exclusion criteria	1a	None	Frequency and percentage of subjects	Not Applicable	Numbers reported
Treatment pattern	All patients meeting inclusion and exclusion criteria	1b	None	Frequency and percentage of subjects	Not Applicable	Numbers reported
Treatment Regime	All patients meeting inclusion and exclusion criteria	1b	None	Frequency and percentage of subjects	Not Applicable	Numbers reported
Time to rwOS, months	All patients meeting inclusion and exclusion criteria	2	125mg starting dose	Kaplan-Meier and Cox proportional hazards model	Factors defined in section 7.1	Censored
Time to rwPFS, months	All patients meeting inclusion and exclusion criteria	2	- Metastasis status - 125mg starting dose	Kaplan-Meier and Cox proportional hazards model	Factors defined in section 7.1	Censored
Time to rwTTD, months	All patients meeting inclusion and exclusion criteria	2	125mg starting dose	Kaplan-Meier and Cox proportional hazards model	Factors defined in section 7.1	Censored

PFIZER CONFIDENTIAL

CCI

Time to rwTTNT, months	All patients meeting inclusion and exclusion criteria	2	125mg starting dose	Kaplan-Meier and Cox proportional hazards model	Factors defined in section 7.1	Censored
Time to rwTTC, months	All patients meeting inclusion and exclusion criteria	2	125mg starting dose	Kaplan-Meier and Cox proportional hazards model	Factors defined in section 7.1	Censored
Time to rwTTDA, months	All patients meeting inclusion and exclusion criteria	2	125mg starting dose	Kaplan-Meier and Cox proportional hazards model	Factors defined in section 7.1	Censored

PFIZER CONFIDENTIAL

CCI

8 LIST OF TABLES AND TABLE SHELLS

Data in the tables will be presented using the following formatting guidelines. Means will be presented to 1 decimal place greater than the precision of the collected variable.

Standard deviations will be presented to 2 decimal places greater than the precision of the collected variable. Medians, 25th percentiles, 75th percentiles, minimums and maximums will be presented to the same precision as collected. Percentages will be presented to 1 decimal place. P-values will be displayed to 4 decimal places.

8.1 Objective 1: Demographic Characteristics, Clinical Characteristics and Treatment Patterns

8.1.1 Demographic Data Demographic Characteristics

Table 15.1.1. Patient Attrition

Criterion	Description	N Included	N Excluded
XXXXXXXXXX	XXXXXXXXXX	xxx	xxx
XXXXXXXXXX	XXXXXXXXXX	xxx	xxx
XXXXXXXXXX	XXXXXXXXXX	xxx	xxx
XXXXXXXXXX	XXXXXXXXXX	xxx	xxx
XXXXXXXXXX	XXXXXXXXXX	xxx	xxx
XXXXXXXXXX	XXXXXXXXXX	xxx	xxx

PFIZER CONFIDENTIAL

[figure not shown]

Table 15.1.2. Baseline Demographic Characteristics at Initial HR+/HER2- A/MBC Diagnosis

Variable/Statistic	palbociclib + AI (n=xxx)
Year of initial diagnosis	
n	xx
Median (Q1, Q3)	xxxx (xxxx, xxxx)
Min, Max	xxxx, xxxx
Year of metastatic diagnosis	
n	xx
Median (Q1, Q3)	xxxx (xxxx, xxxx)
Min, Max	xxxx, xxxx
Year of AMBC diagnosis	
n	xx
Median (Q1, Q3)	xxxx (xxxx, xxxx)
Min, Max	xxxx, xxxx
Age (years) at initial diagnosis	
n	xx
Mean (SD)	x.x (x.xx)
Median (Q1, Q3)	x.x (x.x, x.x)
Min, Max	x.x, x.x
Age category (years) at initial diagnosis, n (%)	
<50	n (x.x%)
50-64	n (x.x%)
65-74	n (x.x%)
≥75	n (x.x%)
Age (years) at A/MBC diagnosis	
n	xx
Mean (SD)	x.x (x.xx)
Median (Q1, Q3)	x.x (x.x, x.x)
Min, Max	x.x, x.x

PFIZER CONFIDENTIAL

Table 15.1.2. Baseline Demographic Characteristics at Initial HR+/HER2- A/MBC Diagnosis

Variable/Statistic	palbociclib + AI (n=xxx)
Age category (years) at A/MBC diagnosis, n (%)	
<50	n (x.x%)
50-64	n (x.x%)
65-74	n (x.x%)
≥75	n (x.x%)
Age (years) at start of palbociclib treatment	
n	xx
Mean (SD)	x.x (x.xx)
Median (Q1, Q3)	x.x (x.x, x.x)
Min, Max	x.x, x.x
Age category (years) at start of palbociclib treatment, n (%)	
<50	n (x.x%)
50-64	n (x.x%)
65-74	n (x.x%)
≥75	n (x.x%)
Age category (years) at death, n (%)	
<50	n (x.x%)
50-64	n (x.x%)
65-74	n (x.x%)
≥75	n (x.x%)
Alive	n (x.x%)
Sex, n (%)	
Male	n (x.x%)
Female	n (x.x%)
Transsexual	n (x.x%)
Other	n (x.x%)
Not Provided	n (x.x%)
Race, n (%)	
American Indian/Alaska Native	n (x.x%)
Asian	n (x.x%)
Black/African American/Native Hawaiian/Pacific Islander	n (x.x%)
White	n (x.x%)
Not Provided	n (x.x%)
Other	n (x.x%)
Ethnicity, n (%)	
Non-Hispanic/Non-Latino	n (x.x%)
Hispanic/Latino	n (x.x%)
Unknown	n (x.x%)
Insurance Category, n (%)	
Medicare/Medicaid	n (x.x%)
Commercial	n (x.x%)
Commercial and Medicare/Medicaid	n (x.x%)
None	n (x.x%)
Not Provided	n (x.x%)
Menopausal Status, n (%)	
Premenopausal	n (x.x%)
Postmenopausal	n (x.x%)

PFIZER CONFIDENTIAL

Table 15.1.2. Baseline Demographic Characteristics at Initial HR+/HER2- A/MBC Diagnosis

Variable/Statistic	palbociclib + AI (n=xxx)
Perimenopausal	n (x.x%)
Unknown	n (x.x%)
Not applicable	n (x.x%)
Region of Residence at A/MBC diagnosis, n (%)	
Northeast	n (x.x%)
Midwest	n (x.x%)
South	n (x.x%)
West	n (x.x%)

PFIZER CONFIDENTIAL

Clinical Characteristics and Comorbidities

Table 15.1.3. Clinical Characteristics and Comorbidities

Variable/Statistic	palbociclib + AI (n=xxx)
Stage at Initial Breast Cancer Diagnosis, n (%)	
Stage 0	n (x.x%)
Stage I	n (x.x%)
Stage IA	n (x.x%)
Stage IB	n (x.x%)
Stage II	n (x.x%)
Stage IIA	n (x.x%)
Stage IIB	n (x.x%)
Stage III	n (x.x%)
Stage IIIA	n (x.x%)
Stage IIIB	n (x.x%)
Stage IIIC	n (x.x%)
Stage IV	n (x.x%)
Unable to stage	n (x.x%)
Not found	n (x.x%)
Not Applicable	n (x.x%)
Histology, n (%)	
Adenoid cystic	n (x.x%)
Cribiform	n (x.x%)
Ductal	n (x.x%)
Inflammatory	n (x.x%)
Intraductal	n (x.x%)
Lobular	n (x.x%)
Medullary with lymphoid stroma	n (x.x%)
Medullary	n (x.x%)
NOS	n (x.x%)
Mucinous	n (x.x%)
Paget's disease and infiltrating	n (x.x%)
Paget's disease and intraductal	n (x.x%)
Papillary	n (x.x%)
Secretory	n (x.x%)
Squamous cell	n (x.x%)
Tubular	n (x.x%)
Performance Status at A/MBC diagnosis (ECOG Score), n (%)	
Sub-total	n (x.x%)
0	n (x.x%)
1	n (x.x%)
2	n (x.x%)
3	n (x.x%)
4	n (x.x%)
Undocumented	n (x.x%)
Total comorbidities, n (%)	
0	n (x.x%)
1	n (x.x%)
2	n (x.x%)
≥3	n (x.x%)
Charlson Comorbidity Index (CCI), n (%)	
0	n (x.x%)
1	n (x.x%)
2	n (x.x%)

PFIZER CONFIDENTIAL

Table 15.1.3. Clinical Characteristics and Comorbidities

Variable/Statistic	palbociclib + AI (n=xxx)
3	n (x.x%)
≥4	n (x.x%)
Time to Metastasis, n (%)	
≤12 months	n (x.x%)
13-24 months	n (x.x%)
25-36 months	n (x.x%)
>36 months	n (x.x%)
De novo metastatic	n (x.x%)
Disease free Interval, n (%)	
≤12 months	n (x.x%)
13-24 months	n (x.x%)
25-36 months	n (x.x%)
>36 months	n (x.x%)
De novo metastatic	n (x.x%)
Disease Free Interval (months)	
n	xx
Mean (SD)	x.x (x.xx)
Median (Q1, Q3)	x.x (x.x, x.x)
Min, Max	x.x, x.x
Metastatic Group, n (%)	
De novo	n (x.x%)
Recurrent	n (x.x%)

Table 15.1.4 Comorbidities Occurring in at Least 5% of Patients

Variable, n (%)	palbociclib + AI (n=xxx)
XXX	n (x.x%)

Comorbidities presented in descending order of frequency

PFIZER CONFIDENTIAL

Table 15.1.5. Summary of Sites of distant metastasis and disease burden at A/MBC diagnosis

Variable, n (%)	palbociclib + AI (n=xxx)
Number of distant metastatic sites	
1	n (x.x%)
2	n (x.x%)
≥3	n (x.x%)
Sites of distant metastasis: bone only	
Yes	n (x.x%)
No	n (x.x%)
Sites of distant metastasis: visceral	
Yes	n (x.x%)
No	n (x.x%)
Disease Burden: Metastatic Sites in Liver	
Multiple lesions	n (x.x%)
No metastasis at site	n (x.x%)
Single lesion	n (x.x%)
Unknown number of lesions	n (x.x%)
Disease Burden: Metastatic Sites in Lung	
Bilateral lungs	n (x.x%)
No metastasis at site	n (x.x%)
Single lung	n (x.x%)
Unknown single bilateral status	n (x.x%)
Disease Burden: Metastatic Sites in Bone	
Multiple sites	n (x.x%)
No metastasis at site	n (x.x%)
Single site	n (x.x%)
Unknown number of sites	n (x.x%)

PFIZER CONFIDENTIAL

Table 15.16. Sites of distant metastasis at A/MBC diagnosis

Variable, n (%)	palbociclib + AI (n=xxx)
Bone (Bone only or in addition to other sites)	n (x.x%)
Bone only	n (x.x%)
Chest wall	n (x.x%)
Contralateral breast	n (x.x%)
Distant Lymph node(s)	n (x.x%)
Visceral Sites	n (x.x%)
Liver	n (x.x%)
Lung	n (x.x%)
Peritoneum	n (x.x%)
Pleural nodules	n (x.x%)
Malignant pleural effusion	n (x.x%)
Skin	n (x.x%)
Brain*	n (x.x%)
Ovary	n (x.x%)
Other: Specify	n (x.x%)
Adrenal	n (x.x%)
Bone marrow	n (x.x%)
Colon	n (x.x%)
Fallopian tubes	n (x.x%)
Omentum	n (x.x%)
Parotid gland	n (x.x%)
Soft tissue	n (x.x%)
Stomach	n (x.x%)

*Includes both brain and spinal metastasis

PFIZER CONFIDENTIAL

Table 15.1.7. Systemic Therapy, Endocrine Therapy and Sensitivity in the Adjuvant Setting

Variable, n (%)	palbociclib + AI (n=xxx)
Adjuvant Systemic Therapy	
Yes	n (x.x%)
No	n (x.x%)
Endocrine Therapy: Yes	n (x.x%)
Endocrine Sensitivity: Yes	n (x.x%)
Endocrine Sensitivity: No	n (x.x%)
Endocrine Therapy: No	n (x.x%)

Table 15.1.8. Endocrine Resistance

Variable, n (%)	palbociclib + AI (n=xxx)
Primary Endocrine Resistance	
Yes	n (x.x%)
No	n (x.x%)
Secondary Endocrine Resistance	
Yes	n (x.x%)
No	n (x.x%)

Table 15.1.9. Follow-up Times in Months

Variable	palbociclib + AI (n=xxx)
Minimum, Maximum	xx.x, xx.x
25 th percentile	xx.x
Median	xx.x
75 th percentile	xx.x

PFIZER CONFIDENTIAL

Biomarkers

Table 15.1.10. HER2, ER and PR Status

Variable, n (%)	palbociclib + AI (n=xxx)
HER2 Status	
Negative	n (x.x%)
Discordant*	n (x.x%)
ER Status	
Positive	n (x.x%)
Negative	n (x.x%)
Unequivocal	n (x.x%)
Unknown	n (x.x%)
PR Status	
Positive	n (x.x%)
Negative	n (x.x%)
Unequivocal	n (x.x%)
Unknown	n (x.x%)

*Discordant HER2 status represents patients who have ISH and IHC tests with differing results that can not be otherwise adjudicated programmatically (ie ISH = Negative and IHC = Positive)

PFIZER CONFIDENTIAL

Table 15.1.11. HR2 and HER2 Specimen and Report Dates

Variable/Statistic	palbociclib + AI (n=xxx)
Year of HR Specimen	
n	xx
Median (Q1, Q3)	xxxx (xxxx, xxxx)
Min, Max	xxxx, xxxx
Year of HR Report	
n	xx
Median (Q1, Q3)	xxxx (xxxx, xxxx)
Min, Max	xxxx, xxxx
Year of HER2 Specimen	
n	xx
Median (Q1, Q3)	xxxx (xxxx, xxxx)
Min, Max	xxxx, xxxx
Year of HER2 Report	
n	xx
Median (Q1, Q3)	xxxx (xxxx, xxxx)
Min, Max	xxxx, xxxx

PFIZER CONFIDENTIAL

Table 15.1.12. BRCA Mutation Results

Variable/Statistic	palbociclib + AI (n=xxx)
BRCA1, n (%)	
Not tested	n (x.x%)
Tested	n (x.x%)
Mutation Not Detected	n (x.x%)
Mutated	n (x.x%)
BRCA2, n (%)	
Not tested	n (x.x%)
Tested	n (x.x%)
Mutation Not Detected	n (x.x%)
Mutated	n (x.x%)
BRCA1 Rearrangement, n (%)	
Not tested	n (x.x%)
Tested	n (x.x%)
Not Detected	n (x.x%)
Negative	n (x.x%)
Year of BRCA Report	
n	xx
Median (Q1, Q3)	xxxx (xxxx, xxxx)
Min, Max	xxxx, xxxx

PFIZER CONFIDENTIAL

Previous Treatment Modalities

Table 15.1.13. Treatment Received Prior to A/MBC diagnosis

Variable, n (%)	palbociclib + AI (n=xxx)
Breast Surgery	
Yes	n (x.x%)
1	n (x.x%)
2	n (x.x%)
≥ 3	n (x.x%)
No	n (x.x%)
Breast Surgery Before Metastasis	
Yes	n (x.x%)
1	n (x.x%)
2	n (x.x%)
≥ 3	n (x.x%)
No	n (x.x%)
Breast Surgery After Metastasis	
Yes	n (x.x%)
1	n (x.x%)
2	n (x.x%)
≥ 3	n (x.x%)
No	n (x.x%)
Breast Radiation Therapy	
Yes	n (x.x%)
1	n (x.x%)
2	n (x.x%)
≥ 3	n (x.x%)
No	n (x.x%)
Breast Radiation Therapy Before Metastasis	
Yes	n (x.x%)
1	n (x.x%)
2	n (x.x%)
≥ 3	n (x.x%)
No	n (x.x%)
Breast Radiation Therapy After Metastasis	
Yes	n (x.x%)
1	n (x.x%)
≥ 2	n (x.x%)
No	n (x.x%)
Chemotherapy	
Yes	n (x.x%)
No	n (x.x%)
Hormone therapy	
Yes	n (x.x%)
No	n (x.x%)

PFIZER CONFIDENTIAL

Table 15.1.14. Breast Surgery Types Before and After Metastasis

Variable, n (%)	Before Metastasis (n=xxx)	After Metastasis (n=xxx)	Overall (n=xxx)
Lumpectomy / excisional biopsy	n (x.x%)	n (x.x%)	n (x.x%)
Mastectomy, NOS	n (x.x%)	n (x.x%)	n (x.x%)
Modified radical mastectomy	n (x.x%)	n (x.x%)	n (x.x%)
Partial mastectomy	n (x.x%)	n (x.x%)	n (x.x%)
Radical mastectomy	n (x.x%)	n (x.x%)	n (x.x%)
Segmental mastectomy	n (x.x%)	n (x.x%)	n (x.x%)
Subcutaneous mastectomy	n (x.x%)	n (x.x%)	n (x.x%)
Surgery, NOS	n (x.x%)	n (x.x%)	n (x.x%)
Total mastectomy	n (x.x%)	n (x.x%)	n (x.x%)

Numbers based on the surgery counts. Patients may have more than one surgery.

PFIZER CONFIDENTIAL

Table 15.1.15. Radiation Body Sites Before and After Metastasis

Variable, n (%)	Before Metastasis (n=xxx)	After Metastasis (n=xxx)	Unknown Radiation Date (n=xxx)	Overall (n=xxx)
Chest wall	n (x.x%)	n (x.x%)	n (x.x%)	n (x.x%)
Chest wall, regional lymph nodes	n (x.x%)	n (x.x%)	n (x.x%)	n (x.x%)
Partial breast	n (x.x%)	n (x.x%)	n (x.x%)	n (x.x%)
Regional lymph nodes	n (x.x%)	n (x.x%)	n (x.x%)	n (x.x%)
Unknown	n (x.x%)	n (x.x%)	n (x.x%)	n (x.x%)
Whole breast	n (x.x%)	n (x.x%)	n (x.x%)	n (x.x%)
Whole breast, regional lymph nodes	n (x.x%)	n (x.x%)	n (x.x%)	n (x.x%)
Chest wall	n (x.x%)	n (x.x%)	n (x.x%)	n (x.x%)
Chest wall, regional lymph nodes	n (x.x%)	n (x.x%)	n (x.x%)	n (x.x%)

Numbers based on the radiation counts. Patients may have more than one radiation therapy.

PFIZER CONFIDENTIAL

Prior Progression and Recurrence

Table 15.1.16. Progression and Recurrence Prior to Start of 1L Therapy for A/MBC Diagnosis

Variable, n (%)	palbociclib + AI (n=xxx)
Progression Before Start of 1L Therapy for A/MBC	
Yes	n (x.x%)
1	n (x.x%)
2	n (x.x%)
≥3	n (x.x%)
No	n (x.x%)
Progression Before Metastasis	
Yes	n (x.x%)
1	n (x.x%)
2	n (x.x%)
≥3	n (x.x%)
No	n (x.x%)
Recurrence Before Start of 1L Therapy for A/MBC	
Yes	n (x.x%)
1	n (x.x%)
2	n (x.x%)
≥3	n (x.x%)
No	n (x.x%)
Recurrence Before Metastasis	
Yes	n (x.x%)
1	n (x.x%)
2	n (x.x%)
≥3	n (x.x%)
No	n (x.x%)

PFIZER CONFIDENTIAL

Table 15.1.17. Progression Details Prior to Start of 1L Therapy for A/MBC diagnosis

Variable, n (%)	palbociclib + AI (n=xxx)
Progression Test Source	
Imaging	n (x.x%)
Imaging confirmed by biopsy	n (x.x%)
Unknown	n (x.x%)
Clinical Confirmation of Progression	
Care Everywhere	n (x.x%)
Discharge Summary	n (x.x%)
External Lab Report	n (x.x%)
Imaging Report	n (x.x%)
Media/scanned doc	n (x.x%)
Medical Oncology Note/Consult	n (x.x%)
Nursing Note	n (x.x%)
Other	n (x.x%)
Progress Note	n (x.x%)
Radiation Oncology Note / Consult	n (x.x%)
Surgical Note	n (x.x%)
Progression Linked to Therapy	
Yes	n (x.x%)
No	n (x.x%)

Numbers based on the progression counts. Patients may have more than one progression prior to A/MBC diagnosis.

PFIZER CONFIDENTIAL

Table 15.1.18. Recurrence Details Prior to Start of 1L Therapy for A/MBC diagnosis

Variable, n (%)	palbociclib + AI (n=xxx)
Recurrence Site	
Distant	n (x.x%)
Local	n (x.x%)
Regional	n (x.x%)
Recurrence Test Source	
Biopsy	n (x.x%)
Imaging	n (x.x%)
Imaging confirmed by biopsy	n (x.x%)
Unknown	n (x.x%)
Clinical Confirmation of Progression	
Care Everywhere	n (x.x%)
Discharge Summary	n (x.x%)
External Lab Report	n (x.x%)
Imaging Report	n (x.x%)
Media/scanned doc	n (x.x%)
Medical Oncology Note/Consult	n (x.x%)
Nursing Note	n (x.x%)
Other	n (x.x%)
Progress Note	n (x.x%)
Radiation Oncology Note / Consult	n (x.x%)
Surgical Note	n (x.x%)
Recurrence Linked to Therapy	
Yes	n (x.x%)
No	n (x.x%)

Numbers based on the recurrence counts. Patients may have more than one recurrence prior to A/MBC diagnosis.

PFIZER CONFIDENTIAL

